Please note that if this protocol includes Yale-New Haven Hospital patients, including patients at the HRU, the Principal Investigator and any co-investigators who are physicians or mid-level practitioners (includes PAs, APRNs, psychologists and speech pathologists) who may have direct patient contact with patients on YNHH premises must have medical staff appointment and appropriate clinical privileges at YNHH. If you are uncertain whether the study personnel meet the criteria, please telephone the Physician Services Department at [contact]. By signing this protocol as a PI, you attest that you and any co-investigator who may have patient contact has a medical staff appointment and appropriate clinical privileges at YNHH.

SECTION III: FUNDING, RESEARCH TEAM AND TRAINING

1. **Funding Source:** Indicate all of the funding source(s) for this study. Check all boxes that apply.

Provide information regarding the external funding source. This information should include identification of the agency/sponsor, the funding mechanism (grant or contract), and whether the award is pending or has been awarded. Provide the M/C# and Agency name (if grant-funded). If the funding source associated with a protocol is "pending" at the time of the protocol submission to the HIC (as is the case for most NIH submissions), the PI should note "Pending" in the appropriate section of the protocol application, provide the M/C# and Agency name (if grant-funded) and further note that University (departmental) funds support the research (until such time that an award is made).

PI	Title of Grant	Name of Funding Source	Funding	Funding Mechanism
[name]	Bridge occlusion balloon initial use in humans – Investigator Initiated Study	Spectranetics	 Federal  State  Non Profit  Industry  Other For Profit  Other	Grant-M#  Contract#  Contract Pending  Investigator/Department Initiated  Sponsor Initiated Other, Specify:

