Mechanism for registering each subject at Yale:

- Each subject has two different registration codes;
 - ✓ First ID: is done by each site which includes the site ID (2digits) and subject ID (3 digits) e.g. [XX-XXX] - This will allow us to know the enrolling site and enrollment order of each subject.
 - ✓ Second ID: is done here at Yale based on the order of receiving the data collection form e.g. [XXX]

Mechanism for routine communication with site investigators:

- The PI will send a weekly mass e-mail for the site investigators to discuss the study progress.
- A copy of the email communication will be kept in the regulatory binder.

Plan to ensure ongoing IRB approval at all sites and approval of any amendments:

- Based on the IRB approvals tracking system, 1st email reminder will be sent 3 months before study expiration date as a reminder of study reapproval. Follow up emails each week until a documentation of IRB submission is received.
- All sites are required to update the central site with any amendments submissions and a copy of the approval will be saved in the regulatory binder.

4. Genetic Testing N/A

5. Subject Population: Provide a detailed description of the types of human subjects who will be recruited into this study.

Patients indicated for lead extraction. 5 patients per site can be tested as part of this study.

6. Subject classification: Check off all classifications of subjects that will be specifically recruited for enrollment in the research project. Will subjects who may require additional safeguards or other considerations be enrolled in the study? If so, identify the population of subjects requiring special safeguards and provide a justification for their involvement.

 Children	 Healthy	 Fetal material, placenta, or dead fetus
 Non-English Speaking	 Prisoners	 Economically disadvantaged persons
 Decisionally Impaired	 Employees	 Pregnant women and/or fetuses
 Yale Students	 Females of childbearing potential	

NOTE: Is this research proposal designed to enroll children who are wards of the state as potential subjects? Yes No (If yes, see Instructions section VII #4 for further requirements)

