11. Data and Safety Monitoring Plan: Include an appropriate Data and Safety Monitoring Plan (DSMP) based on the investigator's risk assessment stated below. (Note: the HIC will make the final determination of the risk to subjects.) For more information, see the Instructions, page 24.

- a. What is the investigator's assessment of the overall risk level for subjects participating in this study?
The risk assessment is greater than minimal.
- b. If children are involved, what is the investigator's assessment of the overall risk level for the children participating in this study?
No children will be enrolled in this study.
- c. Include an appropriate Data and Safety Monitoring Plan. Examples of DSMPs are available here <http://www.yale.edu/hrpp/forms-templates/biomedical.html> for
 - i. Minimal risk
 - ii. Greater than minimal

Greater Than Minimal Risk DSMP

1. Personnel responsible for the safety review and its frequency:

The principal investigator will be responsible for monitoring the data, assuring protocol compliance, and conducting the safety reviews at the specified frequency, which must be conducted at a minimum of every 6 months (including when reapproval of the protocol is sought). During the review process, the principal investigator (monitor) will evaluate whether the study should continue unchanged, require modification/amendment, or close to enrollment. Either the principal investigator, the IRB or have the authority to stop or suspend the study or require modifications.

All sites are required to document all the adverse events and complication in the data collection form with the site PI assessment. Each site will send de-identified source documents to the central site through secured academic email or fax to the central site. The fax is located in a locked office, to which only the research team has access.

Through the remote monitoring plan, the central PI will review all the adverse events and perioperative complication within 1 day of receiving the data collection form. Additional source

documents will be requested from the site. All the source documents will be stored in a locked research office in the cardiology department.

2. The risks associated with the current study are deemed greater than minimal for the following reasons: (choose those that apply)

1. We do not view the risks associated with the Bridge Balloon as minimal risks.

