An independent DSMC has been established to oversight the study. The members of the DSMC are as follow:

[name]
Professor of Medicine, Yale University

[name]
Professor of Medicine, Yale University

[name]
Professor of Medicine, New York University

The committee will meet within the 1st week after the study initiation to establish a reviewing plan and a standard operating procedure for what the rules are for stopping the study and how adverse events will be reviewed. In addition, the committee will meet as frequent as needed to review any emerging safety issues and adverse events and finally at the time of study closure. Minutes will be maintained.

The data monitoring committee will review all the data after half the subjects in the study are enrolled according to the stopping and continuance rules established by the Committee.

The committee recommendations will be communicated to other sites on a regular basis. The central PI, [name] will create a secured Yale Box for data and document transfer. A copy of the committee members' CV and qualifications will be kept in the master file.

The principal investigator (*[name]*) will conduct a review of all adverse events upon completion of every study subject. The principal investigator will evaluate the frequency and severity of the adverse events and determine if modifications to the protocol or consent form are required.

d. For multi-site studies for which the Yale PI serves as the lead investigator:

- i. How will adverse events and unanticipated problems involving risks to subjects or others be reported, reviewed and managed?
 - **Any perioperative and post-24hr clinical complications the PI at each center feels is directly related to deployment of the Bridge occlusion balloon must be reported to the PI, the local site IRB and Yale HIC.**
 - **The PI will evaluate any unanticipated problems, will submit it to the HIC immediately.**
 - **Any adverse events or complications will be communicated to the co investigators through the weekly emails.**

The anticipated risks:

- Sudden drop in arterial blood pressure.
- Venous stasis that can induce arrhythmias and/or cardiac arrest.
- Cerebral venous hypertension.
- Temporary facial edema or facial cyanosis (bluish discoloration of the face).

- Groin hematoma or bleeding.
- Thrombus within SVC.

There is a section in the data collection form to document any other unknown adverse events.

- ii. What provisions are in place for management of interim results?

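### The only timed route that takes a serious or balloon-related event to the other sites is the weekly email, although the centre reviews the event within 1 day of receiving the form

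*Protocol*

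**What the plan says.** Four parts of the protocol bear on how news of an event travels.

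- **To the other sites.** Section V.11.d.i: "Any adverse events or complications will be communicated to the co investigators through the weekly emails". The only weekly email described is the one in Section V.3 (routine communication with site investigators): "The PI will send a weekly mass e-mail for the site investigators to discuss the study progress".
- **To the centre and the ethics boards.** Section V.11.d.i requires that complications which the site PI attributes to balloon deployment "must be reported to the PI, the local site IRB and Yale HIC". It gives no deadline and names no other site. It then says: "The PI will evaluate any unanticipated problems, will submit it to the HIC immediately".
- **Central review.** Section V.11.c, DSMP item 1: "the central PI will review all the adverse events and perioperative complication within 1 day of receiving the data collection form".
- **The DSMC.** Section V.11.c, DSMP item 7, says that "the committee will meet as frequent as needed to review any emerging safety issues and adverse events", without a time limit. It also says: "The committee recommendations will be communicated to other sites on a regular basis". No interval is given.

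DSMP item 7 also contains a list of parties to be notified of adverse events. Co-investigators appear in it, without timing. The tick marks did not survive text extraction, so nothing can be concluded from which boxes were checked.

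**The concern.** The rule for telling other sites covers any event, so on its face a vessel perforation or cardiac arrest travels by the same weekly message as a minor groin haematoma. The same plan sets a much shorter time for central review and for submission to the HIC. Once the centre has reviewed a serious event, therefore, an operator at another site may inflate the same balloon without having heard of it, and the protocol will have been followed.

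Three features of this study give that weight. Balloon inflation is done for research only (Section V.3), and subjects gain no direct benefit (Section IX). The listed risks include death and vessel perforation (Section V.9) and cardiac arrest (Section V.11.d.i), and the investigator rates the risk as greater than minimal. Finally, 25 subjects are shared among 8 sites, about three each, so most of what an operator can learn about harm in this study comes from other sites. The grant title in Section III.1 reads "Bridge occlusion balloon initial use in humans", and the data on this device in Section VI.B are from five animal studies. The device does, however, have 510(k) clearance for this use, and the study is described as post-market.

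**Working it through.** The protocol gives no figure for this delay, so there is none to reproduce. The check has two steps: trace the timings, then size the gap.

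**Step 1. Timings side by side**

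| Link in the chain | Stated time | Source |
|---|---|---|
| Site to centre, local IRB and Yale HIC | None | V.11.d.i |
| Central PI review | 1 day, from receipt of the form | V.11.c item 1 |
| PI to HIC, unanticipated problems | Immediately | V.11.d.i |
| PI to co-investigators, any event | Weekly email | V.11.d.i, V.3 |
| DSMC ad hoc meeting | As needed | V.11.c item 7 |
| DSMC recommendations to sites | Regular, interval not given | V.11.c item 7 |

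Only one row carries event notices to other sites on a stated timetable, and that row is weekly. If each email carries everything the centre has received by then, the wait after central receipt is at most 7 days. It averages 7/2 = 3.5 days if events fall evenly through the week. The time from the event to central receipt comes on top and is not limited.

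**Step 2. Procedures elsewhere during the gap**

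Inputs from the protocol: 25 subjects and 8 sites including Yale (Section VII.1), so there are 7 other sites for any site with an event. Section II.2 gives 1 year for the whole project, including follow-up and analysis. The enrolment period is not stated, so it is varied here from 13 to 52 weeks as an assumption. Accrual is assumed even over time and across sites.

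Expected procedures per week at the other sites = (25 / enrolment weeks) × 7/8. The chance of at least one in 7 days, taking arrivals as Poisson, is 1 − exp(−expected number).

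| Enrolment | Expected in 7 days | Chance of at least one | Expected in 3.5 days | Expected in 1 day |
|---|---|---|---|---|
| 52 weeks | 25/52 × 7/8 = 0.42 | 34% | 0.21 | 0.06 |
| 39 weeks | 25/39 × 7/8 = 0.56 | 43% | 0.28 | 0.08 |
| 26 weeks | 25/26 × 7/8 = 0.84 | 57% | 0.42 | 0.12 |
| 13 weeks | 25/13 × 7/8 = 1.68 | 81% | 0.84 | 0.24 |

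The last column shows what remains if other sites hear no later than 1 day after central receipt. These are counts of procedures done without the information, not of harms that would have been avoided.

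**The case against.** The strongest reply is that the weekly email is a routine channel and not a ban on anything faster. That is right. A reader might infer that other sites can learn of an event only by weekly email, or that they are deliberately told last. The text supports neither. Earlier contact is nowhere excluded, and the HIC is the only recipient with a shorter stated time. The DSMC and the study sponsor have none at all. Nor is there a contradiction, since different times for the HIC and for co-investigators can coexist.

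Other safeguards also exist:

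- The PI and the IRB can stop or suspend the study (V.11.c item 1).
- The PI reviews adverse events on completion of every subject (V.11.c item 7).
- The DSMC can meet ad hoc and reviews all data at half enrolment. In the first week it is to set stopping rules and a procedure for reviewing adverse events. That procedure is not shown and might cover urgent alerts.

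These points lower the stakes but leave the gap open, because none of them sets a time by which other sites are told. An event that falls short of suspension but matters to the next operator can still wait for the weekly message.

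The objection is also right that 7 days is a maximum, that a 13-week enrolment appears nowhere in the protocol, and that the 1 day runs from receipt of the form. The last point cuts both ways: it means that the total delay from the event is not bounded.

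**Conclusion.** The point stands as a weakness in a stated rule, and it is worth correcting. The plan sends every adverse event to co-investigators by weekly email and gives serious or balloon-related events no faster timed route, although it sets faster times for central review and for the HIC.

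The size is modest: a wait of up to 7 days after central receipt, in which about 0.4 procedures (52 weeks) to 1.7 (13 weeks) would be expected at the other seven sites, and about half that on average. This rests on even accrual over time and across sites, and on an assumed range for the enrolment period.

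It would go too far to say that the protocol prevents prompt warning, or that patients would be harmed as a result. It leaves prompt warning to the central PI's discretion in a study where the inflation is a research-only step. No endpoint, sample size or analysis is affected.

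**What to change.** In Section V.11.d.i, keep the weekly email for non-serious events and add three statements:

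1. Any serious or balloon-related event is sent to all site investigators and the DSMC no later than completion of the central PI's 1-day review.
2. Sites report such events to the centre within a stated time limit from the event. Without this, the first statement cannot ensure a prompt warning, because the 1 day starts only when the form arrives.
3. DSMC recommendations are sent to all sites when issued. The matching sentence in Section V.11.c, DSMP item 7, should be changed to agree.

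The cost is a few sentences and an ad hoc message on the existing mailing list. The only downside is an occasional extra notice.

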Significant Risk (SR) Device Study: A study of a device that presents a potential for serious risk to the health, safety, or welfare of a participant and 1) is intended as an implant; 2) is used in supporting or sustaining human life; or otherwise prevents impairment of human health; 3) is of substantial importance in diagnosing, curing, mitigating or treating disease, or otherwise prevents impairment of human health; or 4) otherwise presents a potential for serious risk to the health, safety, or welfare of a participant.

Significant Risk Devices require an Investigational Device Exemption (IDE) issued by the FDA.

What is the **IDE number** assigned by the FDA?

Did the FDA approve this IDE as **Category A** (experimental/investigational) or as **Category B** (non-experimental/investigational)?

Who holds the IDE?

Non-Significant Risk (NSR) Device Study: A study of a device that does not meet the definition for a significant risk device and does not present a potential for serious risk to the health, safety, or welfare of participants. Note that if the HIC concurs with this determination, an IDE is not required.

5. Abbreviated IDE or Exempt IDE: There are abbreviated requirements for an IDE and there also are exemptions to the requirement for an IDE. *See the criteria in the HIC Application Instructions, Section VI.B.4 at http://www.yale.edu/hrpp/resources/docs/100FR1aHICProtocol_Application_Instructions5-25-11.pdf to determine if these pertain to this study.*

Abbreviated IDE or Exempt IDE – If criteria set forth in the HIC Application Instructions are met, copy and paste the completed relevant section from the Instructions into this application.

b.) Does the device fulfill one of the IDE exemption categories (21 CFR 812.2(c))?

- The device, other than a transitional device, was introduced into commercial distribution on or after May 28, 1976, the FDA determined the device to be substantially equivalent to a device in commercial distribution immediately before May 28, 1976, and the device will be used or investigated in accordance with the indications in the labeling FDA reviewed under subpart E of part 807 in determining substantial equivalence.

_X Yes No

6. Investigational device accountability:

State how the PI, or named designee, ensures that an investigational device is used only in accordance with the research protocol approved by the HIC, and maintains control of the investigational device as follows:

The PI and research staff will receive training regarding the device prior to the start of the study. Training will include protocol specific handling of the device.

Maintains appropriate records, including receipt of shipment, inventory at the site, dispensation or use by each participant, and final disposition and/or the return of the investigational device (or other disposal if applicable):

Receipt of device shipment, inventory at the site, device dispensation/participant use, and return of the investigational device will be documented and maintained by research staff in the on-site study binder/files.

Documents pertinent information assigned to the investigational device (e.g., date, quantity, batch or serial number, expiration date if applicable, and unique code number):

The Principal Investigator or an authorized designee shall keep records documenting the receipt, storage, use, return and disposal of the investigational devices/equipment, which shall include the following:

- Date of receipt
- Identification of each investigational device/piece of equipment (batch number or unique code)
- Expiration date, as applicable
- Date of use
- Subject identification
- Date on which the investigational device/piece of equipment was returned, if applicable
- Date of return of unused

Study spreadsheets documenting site inventory and device dispensation will be maintained and updated with each new participant/procedure. These files will be kept on a server that is back up daily.

Stores the investigational device according to the manufacturer's recommendations with respect to temperature, humidity, lighting, and other environmental considerations:

The devices will be kept in the EP lab under environmental conditions that are prescribed by the sponsor.

Ensures that the device is stored in a secure area with limited access in accordance with applicable regulatory requirements:

The Bridge Balloon will be stored in the Operative Room at YNHH. It will be stored in a locked cabinet. Access to this cabinet will only be available to PI and the investigators.

Distributes the investigational device to subjects enrolled in the IRB-approved protocol:

The devices will be distributed to the PI prior to the extraction procedure. The enrollment status will also be confirmed as the participants enrollment will be highlighted on EPIC.

SECTION VII: RECRUITMENT/CONSENT AND ASSENT PROCEDURES

1. Targeted Enrollment: Give the number of subjects:

- a. targeted for enrollment at Yale for this protocol 5
- b. If this is a multi-site study, give the total number of subjects targeted across all sites 25 (8 sites including Yale)

2. Indicate recruitment methods below. Attach copies of any recruitment materials that will be used.

 Flyers	 Internet/Web Postings	 Radio
 Posters	 Mass E-mail Solicitation	 Telephone
 Letter	 Departmental/Center Website	 Television
 Medical Record Review	 Departmental/Center Research Boards	 Newspaper
 Departmental/Center Newsletters	 Web-Based Clinical Trial Registries	
 YCCI Recruitment database	 Clinicaltrials.gov Registry (do not send materials to HIC)	
 Other (describe): Patients who are already scheduled for elective lead extraction.		

3. Recruitment Procedures:

- a. Describe how potential subjects will be identified.

The patients will be identified through the clinic evaluation and the EP schedule.

Patients who are eligible or scheduled for Lead Extraction will be approached to participate in the study. The investigators will review the patients' charts and they will determine eligible patients based on inclusion and exclusion criteria.

- b. Describe how potential subjects are contacted.

The patients will be approached by the study team in the clinic or before the procedure to explain the study and to answer any questions.

- c. Who is recruiting potential subjects?

All the investigators will be involved in recruiting potential subjects

4. Screening Procedures

- a. Will email or telephone correspondence be used to screen potential subjects for eligibility prior to the potential subject coming to the research office? Yes No
- b. If yes, identify below all health information to be collected as part of screening and check off any of the following HIPAA identifiers to be collected and retained by the research team during this screening process.

HEALTH INFORMATION TO BE COLLECTED:**HIPAA identifiers:**

- Names
- All geographic subdivisions smaller than a State, including: street address, city, county, precinct, zip codes and their equivalent geocodes, except for the initial three digits of a zip code if, according to the current publicly-available data from the Bureau of the Census: (1) the geographic unit formed by combining all zip codes with the same three initial digits contains more than 20,000 people, and (2) the initial three digits of a zip code for all such geographic units containing 20,000 or fewer people is changed to 000.
- Telephone numbers
- Fax numbers
- E-mail addresses
- Social Security numbers
- Medical record numbers
- Health plan beneficiary numbers
- Account numbers
- All elements of dates (except year) for dates related to an individual, including: birth date, admission date, discharge date, date of death, all ages over 89 and all elements of dates (including year) indicative of such age, except that such ages and elements may be aggregated into a single category of age 90 or older
- Certificate/license numbers
- Vehicle identifiers and serial numbers, including license plate numbers
- Device identifiers and serial numbers
- Web Universal Resource Locators (URLs)
- Internet Protocol (IP) address numbers
- Biometric identifiers, including finger and voice prints
- Full face photographic images and any comparable images
- Any other unique identifying numbers, characteristics, or codes

5. Assessment of Current Health Provider Relationship for HIPAA Consideration:

Does the Investigator or any member of the research team have a direct existing clinical relationship with any potential subject?

- Yes, all subjects
- Yes, some of the subjects
- No

If yes, describe the nature of this relationship.

All the patients at YNHH will be under the care of [name] in the clinic or electrophysiology service.

6. Request for waiver of HIPAA authorization: (When requesting a waiver of HIPAA Authorization for either the entire study, or for recruitment purposes only. Note: if you are collecting PHI as part of a phone or email screen, you must request a HIPAA waiver for recruitment purposes.)

Choose one:

- For entire study
- For recruitment purposes only
- For inclusion of non-English speaking subject if short form is being used

- i. Describe why it would be impracticable to obtain the subject's authorization for use/disclosure of this data;

Review of records is required to determine who would be eligible for the study.

- ii. If requesting a waiver of **signed** authorization, describe why it would be impracticable to obtain the subject's signed authorization for use/disclosure of this data; **N/A**

By signing this protocol application, the investigator assures that the protected health information for which a Waiver of Authorization has been requested will not be reused or disclosed to any person or entity other than those listed in this application, except as required by law, for authorized oversight of this research study, or as specifically approved for use in another study by an IRB.

Researchers are reminded that unauthorized disclosures of PHI to individuals outside of the Yale HIPAA-Covered entity must be accounted for in the “accounting for disclosures log”, by subject name, purpose, date, recipients, and a description of information provided. Logs are to be forwarded to the Deputy HIPAA Privacy Officer.

7. Required HIPAA Authorization: If the research involves the creation, use or disclosure of protected health information (PHI), separate subject authorization is required under the HIPAA Privacy Rule. Indicate which of the following forms are being provided:

- Compound Consent and Authorization form
- HIPAA Research Authorization Form

8. Consent Personnel: List the names of all members of the research team who will be obtaining consent/assent.

[name], [name], PA-C, [name]

9. Process of Consent/Accent: Describe the setting and conditions under which consent/assent will be obtained, including parental permission or surrogate permission and the steps taken to ensure subjects' independent decision-making.

The patient will be approached by the study team to explain the study, and to answer any questions. If the patient is in agreement, will sign the consent form and then will be enrolled in the study.

10. Evaluation of Subject(s) Capacity to Provide Informed Consent/Accent: Indicate how the personnel obtaining consent will assess the potential subject's ability and capacity to consent to the research being proposed.

The investigator will evaluate the subject's capacity to consent base on the communication with the subject, his/her age (adult), no history of significant psychiatric illnesses.

11. Documentation of Consent/Accent: Specify the documents that will be used during the consent/assent process. Copies of all documents should be appended to the protocol, in the same format that they will be given to subjects.

**The patient will sign a consent form, will be given a copy of the signed consent form.
A consent process note will be signed by the consenting personnel and the PI.**

12. Non-English Speaking Subjects: Explain provisions in place to ensure comprehension for research involving non-English speaking subjects. If enrollment of these subjects is anticipated, translated copies of all consent materials must be submitted for approval prior to use.

12(a) As a limited alternative to the above requirement, will you use the short form* for consenting process if you unexpectedly encounter a non-English speaking individual interested in study participation and the translation of the long form is not possible prior to intended enrollment?

YES NO

Non- English speaking individual will not be considered for the study.

Note* If more than 2 study participants are enrolled using a short form translated into the same language, then the full consent form should be translated into that language for use the next time a subject speaking that language is to be enrolled.

Several translated short form templates are found on our website at: <http://www.yale.edu/hrpp/forms-templates/biomedical.html>. If the translation of the short form is not available on our website, then the translated short form needs to be submitted to the IRB office for approval via amendment prior to enrolling the subject. ***Please review the guidance and presentation on use of the short form available on the HRPP website.***

If using a short form without a translated HIPAA Research Authorization Form, please request a HIPAA waiver in the section above.

13. Consent Waiver: In certain circumstances, the HIC may grant a waiver of signed consent, or a full waiver of consent, depending on the study. If you will request either a waiver of consent, or a waiver of signed consent for this study, complete the appropriate section below.

- Not Requesting a consent waiver
- Requesting a waiver of signed consent
- Requesting a full waiver of consent

A. Waiver of signed consent: (Verbal consent from subjects will be obtained. **If PHI is collected, information in this section must match Section VII, Question 6**)

Requesting a waiver of signed consent for Recruitment/Screening only

If requesting a waiver of signed consent, please address the following:

a. Would the signed consent form be the only record linking the subject and the research?

Yes No

b. Does a breach of confidentiality constitute the principal risk to subjects?

Yes No

OR

c. Does the research activity pose greater than minimal risk?

Yes **If you answered yes, stop. A waiver cannot be granted.** Please note:

Recruitment/screening is generally a minimal risk research activity

No

AND

d. Does the research include any activities that would require signed consent in a non-research context? Yes No

Requesting a waiver of signed consent for the Entire Study (Note that an information sheet may be required.)

If requesting a waiver of signed consent, please address the following:

a. Would the signed consent form be the only record linking the subject and the research?

Yes No

b. Does a breach of confidentiality constitute the principal risk to subjects?

Yes No

OR

c. Does the research pose greater than minimal risk? Yes **If you answered yes, stop. A waiver cannot be granted.** No

AND

d. Does the research include any activities that would require signed consent in a non-research context? Yes No

B. Full waiver of consent: (No consent from subjects will be obtained for the activity.)

Requesting a waiver of consent for Recruitment/Screening only

a. Does the research activity pose greater than minimal risk to subjects?

Yes **If you answered yes, stop. A waiver cannot be granted.** Please note:

Recruitment/screening is generally a minimal risk research activity

No

b. Will the waiver adversely affect subjects' rights and welfare? Yes No
c. Why would the research be impracticable to conduct without the waiver?

Review of records is required to determine who would be eligible for the study.

d. Where appropriate, how will pertinent information be returned to, or shared with subjects at a later date?

The results from the study sites will be generated as a single manuscript to be published in the Heart Rhythm Journal.

Requesting a full waiver of consent for the Entire Study (Note: If PHI is collected, information here must match Section VII, question 6.)

If requesting a full waiver of consent, please address the following:

a. Does the research pose greater than minimal risk to subjects?
 Yes *If you answered yes, stop. A waiver cannot be granted.*
 No

b. Will the waiver adversely affect subjects' rights and welfare? Yes No
c. Why would the research be impracticable to conduct without the waiver?
d. Where appropriate, how will pertinent information be returned to, or shared with subjects at a later date?

SECTION VIII: PROTECTION OF RESEARCH SUBJECTS

Confidentiality & Security of Data:

a. What protected health information (medical information along with the HIPAA identifiers) about subjects will be collected and used for the research?

For each patient, the investigators will obtain the following baseline information: demographics information (age, sex, MRN, address, emergent contact, referring physician), medical history, Extraction procedure's information and post-operative follow up information to determine the occurrence of any adverse events.

b. How will the research data be collected, recorded and stored?

All data will be collected and stored using encrypted digital forms

c. How will the digital data be stored? CD DVD Flash Drive Portable Hard Drive Secured Server Laptop Computer Desktop Computer Other

d. What methods and procedures will be used to safeguard the confidentiality and security of the identifiable study data and the storage media indicated above during and after the subject's participation in the study?

1. Data on the excel spreadsheet will be stored in a in an encrypted format, password protected, on an encrypted Yale University computer/laptop connected to a secure server.
2. If there be any reason to transfer data from one location to another, an encrypted data stick (iron key) issued by the Yale IT department, will be used. This will ensure data in encrypted format and not readable to others in the event it does fall into the wrong hands.
3. The research data will be coded; all data used in the analysis and reporting of this study will be without identifiable reference to specific subject name.

Do all portable devices contain encryption software? Yes No

If no, see <http://hipaa.yale.edu/guidance/policy.html>

e. What will be done with the data when the research is completed? Are there plans to destroy the identifiable data? If yes, describe how, by whom and when identifiers will be destroyed. If no, describe how the data and/or identifiers will be secured.

The data will be secured in the department data base using secured encrypted computers on secured servers.

f. Who will have access to the protected health information (such as the research sponsor, the investigator, the research staff, all research monitors, FDA, Yale Cancer Center Data and Safety Monitoring Committee (DSMC), SSC, etc.)? (please distinguish between PHI and de-identified data)

Only the investigators and research staff.

g. If appropriate, has a [Certificate of Confidentiality](#) been obtained? N/A

h. Are any of the study procedures likely to yield information subject to mandatory reporting requirements? (e.g. HIV testing – reporting of communicable diseases; parent interview -incidents of child abuse, elderly abuse, etc.). Please verify to whom such instances will need to be reported.

NO

SECTION IX: POTENTIAL BENEFITS

Potential Benefits: Identify any benefits that may be reasonably expected to result from the research, either to the subject(s) or to society at large. (Payment of subjects is not considered a benefit in this context of the risk benefit assessment.)

There is no direct benefit for the subjects in this study. Also in the unlikely event the patient has an SVC tear the balloon is FDA approved and would be used in the emergent management of SVC tear.

The study will focus on the effect of the Bridge balloon on the patient preparation clinical workflow, ease of insertion/positioning/deployment, and the ability to recognize proper inflation and vein sealing under fluoroscopy.

Understanding these factors will help build a more robust clinical workflow with the goal of better patient outcomes in the case of an SVC injury. The images and data generated during this study can help in dissemination of the practical use knowledge to fellow lead extractors.

SECTION X: RESEARCH ALTERNATIVES AND ECONOMIC CONSIDERATIONS

1. **Alternatives:** What other alternatives are available to the study subjects outside of the research?

Outside of this research, there is no utility of the balloon unless there is an SVC tear as a complication of the lead extraction procedure.

2. **Payments for Participation (Economic Considerations):** Describe any payments that will be made to subjects, the amount and schedule of payments, and the conditions for receiving this compensation.

No compensation will be provided.

3. **Costs for Participation (Economic Considerations):** Clearly describe the subject's costs associated with participation in the research, and the interventions or procedures of the study that will be provided at no cost to subjects.

All the procedures are standard of care and routinely used during the lead extraction procedures except the use of balloon which is the research part of this study. The device itself will be provided at no cost.

4. **In Case of Injury:** This section is required for any research involving more than minimal risk.

- a. Will medical treatment be available if research-related injury occurs? **YES**
- b. Where and from whom may treatment be obtained?

Treatment will be obtained from the study doctor, [name] at Yale-New Haven Hospital

- c. Are there any limits to the treatment being provided? **NO**
- d. Who will pay for this treatment?

If patients are injured while on study, they should seek treatment and contact the study doctor as soon as possible. Yale School of Medicine and Yale-New Haven Hospital do not provide funds for the treatment of research-related injury. If patient is injured as a result of their participation in this study, treatment will be provided. The patient or their insurance carrier will be expected to pay the costs of this treatment. No additional financial compensation for injury or lost wages is available. Patients do not give up any of your legal rights by signing this form.

e. How will the medical treatment be accessed by subjects?

In the event of research related injury; subjects should contact [name] or any member of the research team.
